STUDY PROTOCOL AND STATISTICAL ANALYSIS PLAN

Official Title:

**Effects of a Wearable Device and Social Media-Based
Intervention on Physical Activity and Sleep Quality in
Adults: A Randomized Controlled Trial**

NCT Number: NCT06739876

Organization Unique Protocol ID: NCUEREC-110-082

Document Date: August 15, 2025

1. Introduction and Objectives

The objective of this randomized controlled trial (RCT) is to evaluate the efficacy of a wearable device-based intervention, supplemented with social media support, on enhancing physical activity (PA) levels and improving sleep quality among adults. The study specifically investigates whether motivational support via social media (LINE) provides incremental benefits compared to using a wearable device alone.

2. Study Design and Setting

This study employs a three-arm, parallel-group randomized controlled trial design conducted at National Chung Hsing University, Taiwan. A total of 75 participants are randomly assigned to one of three groups in a 1:1:1 ratio.

Arm 1 (Device + Support): Garmin wearable device + motivational support via LINE.

Arm 2 (Device Only): Garmin wearable device only.

Arm 3 (Control Group): No intervention (standard lifestyle).

3. Eligibility Criteria

Inclusion: Healthy adults aged 18-64 who own a smartphone and have not previously used wearable fitness trackers.

Exclusion: Individuals with medical conditions that contraindicate increased physical activity or those currently participating in other PA-related interventions.

4. Detailed Intervention Protocol

Wearable Technology: Participants in Arm 1 and Arm 2 are provided with a Garmin activity tracker. They are instructed to use the "Move Alert" feature, which vibrates to prompt movement after periods of prolonged sitting.

Social Media Support (Arm 1 only): A structured LINE group is

established for:

Weekly Education: Sharing health knowledge regarding the benefits of sleep and PA.

Interactive Support: Research assistants provide tailored feedback via digital stickers and respond to participant inquiries.

5. Outcome Measures

Primary Outcome: Change in Physical Activity (measured by steps/day and sedentary breaks).

Secondary Outcome: Change in Sleep Quality (assessed via standardized sleep quality questionnaires and device-derived sleep metrics).

Assessment Points: Data are collected at Baseline (T0), Post-intervention (T1, 1 month), and Follow-up (T2, 2 months).

6. Statistical Analysis Plan (SAP)

Data will be analyzed using SPSS software.

Descriptive Statistics: Baseline characteristics will be summarized as means (SD) or frequencies.

Main Analysis: A Two-way Mixed ANOVA (3 Groups \times 3 Time points) will be performed to examine the main effects of "Group" and "Time," as well as the Group-by-Time interaction effect on total sedentary time.

Post-hoc Testing: If a significant interaction is found, Bonferroni-adjusted post-hoc tests will be conducted to identify specific differences between groups at each time point.

Significance Level: The alpha level is set at 0.05.

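### Two measures share the primary label and one alpha of 0.05 with no success rule; if either may carry the claim, the false-positive rate can reach 9.75%

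*Combined protocol and SAP*

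**What the plan says.** Section 5 (Outcome Measures) of the combined protocol and SAP gives one primary outcome with two component measures: "Primary Outcome: Change in Physical Activity (measured by steps/day and sedentary breaks". It does not rank the measures, combine them, or say what pattern of results counts as success.

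Section 6 (Statistical Analysis Plan) gives one error level for the whole plan: "Significance Level: The alpha level is set at 0.05". It states no split or testing order across measures, and does not state sidedness.

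The only multiplicity step is the post-hoc one: "If a significant interaction is found, Bonferroni-adjusted post-hoc tests will be conducted to identify specific differences between groups at each time point". That concerns pairs of groups at a time point within one analysed variable. It does not reach across outcome measures.

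The only model specified is a mixed ANOVA of three groups by three time points, and the variable it names is a different one: the "Group-by-Time interaction effect on total sedentary time". No test is written down for steps/day or for sedentary breaks.

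**The concern.** Steps/day measures how much a person moves; sedentary breaks measure how often sitting is interrupted. They can disagree. The tracker's Move Alert acts on sitting directly, and a short interruption need not change the daily step count much. A trial in which breaks differ between arms and steps do not is therefore plausible, as is the reverse.

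The plan gives no way to read such a result. If one significant measure is enough, there are two chances at 0.05 to claim success, and the stated 5% does not hold for the pair. If both are needed, there is no inflation, but a split result is a negative trial. With neither rule written down, the choice can be made after the data are seen.

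**Working it through.** **Inputs from the documents.** Two primary measures (Section 5). Alpha 0.05 (Section 6). 75 participants allocated 1:1:1, so 75/3 = 25 per arm (Section 2). Three time points (Section 5).

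**Assumptions.** The documents give no correlation ρ between the two measures, so a range is shown. Two-sided tests are assumed for the normal calculation.

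**The plan's own figure.** The 0.05 is set, not derived, so there is nothing to reproduce. The documents give no effect size, standard deviation or power from which to rebuild the sample size.

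**Either-measure rule, independent tests.** P(at least one false positive) = 1 − (1 − 0.05)² = 1 − 0.9025 = 0.0975, which is 0.0975/0.05 = 1.95 times the stated level.

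**Either-measure rule, correlated tests.** P(either) = 0.05 + 0.05 − P(both). P(both) comes from a bivariate normal distribution with correlation ρ. At ρ = 0.5, for example, 0.10 − 0.0093 = 0.0907.

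**Check on the plan's type of test.** The group-by-time F-test has (3 − 1)(3 − 1) = 4 numerator and (75 − 3)(3 − 1) = 144 denominator degrees of freedom. It was simulated on two correlated outcomes with no true effect: 100,000 trials per ρ, 25 per arm, three time points, and an assumed within-person correlation of 0.5. A single test rejected in 4.9% to 5.1% of trials, as it should.

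| Assumed ρ | P(both), normal | P(either at 0.05), normal | P(either at 0.05), simulated F | P(either at 0.025), normal |
|---|---|---|---|---|
| 0 | 0.0025 | 0.0975 | 0.0967 | 0.0494 |
| 0.3 | 0.0049 | 0.0951 | 0.0951 | 0.0484 |
| 0.5 | 0.0093 | 0.0907 | 0.0928 | 0.0465 |
| 0.7 | 0.0165 | 0.0835 | 0.0853 | 0.0430 |
| 0.8 | 0.0219 | 0.0781 | 0.0804 | 0.0402 |
| 0.9 | 0.0296 | 0.0704 | 0.0729 | 0.0362 |

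The simulated F-tests agree closely with the normal calculation, so the size of the problem does not depend on which is used.

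**Both-measures rule.** If at least one measure has no true effect, the chance that both reject cannot exceed the chance that this one rejects, which is 0.05. The rate is therefore at most 5% with no split. With no effect on either measure it is the P(both) column, 0.0025 to 0.0296.

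**Holm across the two.** The smaller p-value is compared with 0.025 and, if that succeeds, the larger with 0.05. With no effect on either measure, the chance of any false claim is the last column, bounded by 0.025 + 0.025 = 0.05. If only one measure has no effect, its threshold never exceeds 0.05. The 5% level holds in every case.

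**The case against.** The strongest reply is that the documents never state an either-measure rule. Section 5 joins the two measures with a conjunction, which can be read as requiring both, and then nothing is inflated. A reader might infer that the plan's false-positive rate simply is nearly doubled. The documents do not support that. It needs an either-measure rule, which is unstated, and a correlation that is at most moderate, which is unknown. At correlations of 0.8 to 0.9 the rate is about 7% to 8%. This part of the objection stands, and the figures above are conditional for that reason. It does not remove the gap: the conjunction lists what is measured and does not define success, so the either-measure reading remains open.

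A second reply is that the arithmetic describes two tests the SAP does not contain, since its one model is for total sedentary time. That is correct as a description. It leaves more room for choice rather than less, because no test is fixed for either named primary measure. A reader might go further and count sedentary time as a third route to a primary claim, giving 1 − 0.95³ = 14.3% if independent. The documents do not support that either: Section 5 does not list sedentary time as primary, and Section 6 does not say that its result decides the primary question.

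A third reply concerns the remedy. A fixed sequence with steps/day first would also keep 5%, but nothing in the documents puts steps ahead of breaks, and Move Alert acts more directly on breaks. That stands, and the fix below does not impose an order.

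**Conclusion.** The gap is real and conditional in size. The plan has two primary measures, one alpha, no success rule, and no adjustment across the measures. If either measure may carry the primary claim at 0.05, the false-positive rate can reach 9.75% under independence, and is about 9.1%, 8.4% and 7.0% at assumed correlations of 0.5, 0.7 and 0.9. If both are required, it is at or below 5%. The documents do not say which rule applies, so the supported conclusion is that 5% control is not assured, not that it has been lost.

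These sizes rest on the assumed correlations and two-sided tests, with the simulation as a check on the F-test. The absence of a success rule rests on no assumption. The change is worth making because it decides what counts as a positive trial and is cheap.

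**What to change.** Before results by arm are seen, add one of these rules to Section 6:

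- **Holm.** Test the group-by-time interaction for steps/day and for sedentary breaks, with Holm across the two (0.025, then 0.05). This suits two measures of equal importance and needs no order between them.
- **Both required.** The primary claim needs both interactions significant at 0.05.
- **Single primary.** Name one of the two as the primary measure, tested at 0.05, and make the other secondary.

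In the same edit, apply the Main Analysis to the chosen measure or measures and make total sedentary time a non-primary analysis. A success rule alone would leave no model attached to either primary measure. The existing Bonferroni step for group comparisons can stay, applied within each measure once its interaction has passed its threshold.

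The cost is a few sentences in Section 6, with no new data and no more participants. Holm makes the first threshold slightly stricter. The both-measures rule lowers power, and a split result then counts as negative. A single primary measure means the other cannot carry a confirmatory claim. The loss of power cannot be quantified from the documents, which give no effect size or standard deviation.

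### The mixed ANOVA, run the usual way in SPSS, keeps only participants with all three visits: observed data are lost, and group contrasts can be biased in either direction

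*Combined protocol and SAP*

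**What the plan says.** Section 2 sets the size and allocation: "A total of 75 participants are randomly assigned to one of three groups in a 1:1:1 ratio", which is 25 per arm. Section 5 sets three assessments: "Data are collected at Baseline (T0), Post-intervention (T1, 1 month), and Follow-up (T2, 2 months".

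Section 6 says "Data will be analyzed using SPSS software" and does not name the procedure. The main analysis begins "Main Analysis: A Two-way Mixed ANOVA (3 Groups" and crosses group with three time points. It tests both main effects "as well as the Group-by-Time interaction effect on total sedentary time". If the interaction is significant, "Bonferroni-adjusted post-hoc tests will be conducted to identify specific differences between groups at each time point". On significance it says only "The alpha level is set at 0.05".

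No section mentions dropout, missing values, imputation, an analysis population, a sensitivity analysis or a sphericity correction.

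**The concern.** A classical two-way mixed ANOVA needs a complete row for each person. The usual SPSS implementation (GLM Repeated Measures) removes incomplete rows listwise. Someone with T0 and T1 but no T2 therefore disappears from the whole analysis, including the T1 comparison to which that person contributed data. Because the SAP states no rule, this default decides who is analysed.

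Two things are at stake. The first is information, in a trial with only 25 per arm. The second is the randomised comparison. The arms make different demands (device plus LINE group, device only, nothing), so people may leave at different rates or for different reasons by arm. The main question, what LINE adds to the device, rests on Arm 1 against Arm 2.

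**Working it through.** **Inputs.** From the documents: 75 randomised 1:1:1, so 75/3 = 25 per arm; three visits; a 3 x 3 mixed ANOVA in SPSS. The documents give no dropout rate, SD, correlation or effect size. Everything else below is assumed: SD 1, within-person correlation 0.6 unless stated, true effect 0.50 SD or none, loss of 10% to 20%. The plan has no figure of its own to reproduce.

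**1. Data loss.**

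- Missing T2 only, proportion p: completers = 75(1 - p); measurements discarded = 2 x 75p, because T0 and T1 of each leaver are dropped. At 10%: 67.5 completers on average, 15 measurements discarded. At 20%: 75 x 0.8 = 60 completers, 2 x 15 = 30 discarded, out of 75 + 75 + 60 = 210 collected.
- Missing T1 and T2 independently, each with probability p: completers = 75(1 - p)². At 10%: 75 x 0.81 = 60.75. At 20%: 75 x 0.64 = 48. In the latter case 3 x 48 = 144 of 75 + 60 + 60 = 195 collected measurements are used, or 74%.

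**2. Precision under random loss.** The variance of a T0-to-T1 change is 2(1 - 0.6) = 0.8. The standard error of a two-arm contrast in change is √(2 x 0.8/n).

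- All T1 values used, n = 25: √0.064 = 0.253.
- Completers after 20% loss at T2, n = 20: √0.080 = 0.283.

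Simulation of 8,000 trials agrees: 0.251 using all data against 0.284 in completers. For the T2 contrast the gain is small, 0.272 against 0.281, because T2 itself is missing.

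**3. Bias in one illustration.** Benefit is scored as positive and the true Arm 1 minus Arm 2 effect is 0.50 at T1 and T2. About 20% of Arm 1 leave after T1, mainly those with low T1 values (logistic slope 1.5). Arm 2 loses the same share at random.

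- Completers differ at T1 by 0.73, a shift of 0.73 - 0.50 = 0.23.
- Selection on T1 moves the other visits by correlation x 0.23 = 0.6 x 0.23 = 0.14. Completers therefore differ by about 0.14 at T0, although randomisation made the true difference zero, and by 0.50 + 0.14 = 0.64 at T2 (0.63 to 0.64 in simulation).
- Change from baseline: T1, 0.73 - 0.14 = 0.59; T2, 0.64 - 0.14 = 0.50.
- A likelihood analysis of all observed data gives 0.50 at T1 and 0.49 to 0.50 at T2.

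With correlations T0–T1 0.5, T0–T2 0.3 and T1–T2 0.8, the change contrasts are about 0.61 and 0.57, so the absence of bias at T2 is a product of the equal correlations.

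**4. Other dropout mechanisms.** Here the true effect is -0.50 (less sedentary time), with logistic dropout before T2 of about 14% to 21% per arm and 1,000,000 simulated participants per arm. Completers give:

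| Dropout depends on | Change, T1 | Change, T2 | Raw, T1 | Raw, T2 |
|---|---|---|---|---|
| Baseline, equally in both arms | -0.50 | -0.50 | -0.50 | -0.50 |
| Baseline, in one arm only | -0.43 | -0.43 | -0.61 | -0.61 |
| T1, equally in both arms | -0.48 | -0.50 | -0.45 | -0.47 |
| T1, in one arm only | -0.55 | -0.50 | -0.63 | -0.58 |

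The likelihood estimate of change is -0.50 in every row. When dropout depends on the unseen T2 value in one arm only, both methods are biased for the T2 change: completers -0.55, likelihood -0.57.

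**5. Sphericity.** Correlations of 0.5, 0.3 and 0.8 give epsilon 0.72. In repeated simulations, type I error for the interaction was 6.9% to 7.4% uncorrected and 4.8% to 5.2% with the Greenhouse-Geisser correction.

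**The case against.** The SAP does not name an SPSS procedure, and SPSS has a mixed-model procedure that keeps partial records. That is true, but a two-way mixed ANOVA is not the usual description of that procedure. If it was intended, the SAP should say so. The post-hoc tests might also be run visit by visit on whoever is present. They would then use different participants from the interaction test, which the SAP does not address either.

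A reader might infer that completer analysis will overstate the benefit. The documents do not support this. They give no attrition figure and no reason for leaving, and the table above shows overstatement, understatement and no bias. Dropout that depends equally on baseline in all arms leaves the group contrasts unbiased. Bias needs dependence that differs by arm, or dependence on post-baseline activity when there is a treatment effect.

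A reader might also take 0.73 against 0.50 as the bias in the main test. It is not. The SAP tests the interaction first, which concerns change from baseline. On that scale the excess at T1 is 0.09, not 0.23, and at T2 it is nil under equal correlations. The raw differences matter for the conditional post-hoc tests and the Group main effect.

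Sphericity alone does not justify a new model: SPSS prints the Greenhouse-Geisser row by default, and one sentence would settle which row governs.

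Finally, follow-up lasts only two months, so losses may be small. That limits the size of the problem but does not supply the missing rule.

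**Conclusion.** The point holds in a limited form. As written, with the standard SPSS route, the main analysis is restricted to participants with all three visits, and nothing in the document overrides that. The loss of collected data and of precision at T1 follows directly from any incomplete follow-up; its size depends on a dropout rate that the documents do not give. Bias is possible and plausible given the different demands of the arms, but it is neither certain nor of known direction. In the scenarios tried with dropout driven by observed values, it was at most about 0.1 SD for change from baseline and somewhat over 0.2 SD for raw per-visit differences. Confidence is high for the listwise-deletion mechanism and lower for the magnitudes, which rest on the assumed correlations, effect and dropout models. The change should be made because a better method is available in the same software.

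**What to change.** In section 6, replace the mixed ANOVA with a likelihood-based linear mixed model for repeated measures (SPSS MIXED):

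- Fixed effects group, visit and group-by-visit, with unstructured covariance across visits.
- All observed visits of all randomised participants, analysed as allocated. T0 may stay as an outcome, which retains participants with no follow-up. It may instead be a covariate, but then participants without any follow-up value drop out of the model; the SAP should say which option applies.
- Bonferroni-adjusted group contrasts at T1 and T2 taken from the same model.
- One sensitivity analysis for data missing not at random, since the model removes bias only if data are missing at random. An example is multiple imputation with arm-specific shifts over a stated range.
- Reporting of numbers observed by arm and visit, with reasons for loss.

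Unstructured covariance also removes the sphericity assumption. If the ANOVA is kept, state that the Greenhouse-Geisser row governs, and state how incomplete cases are handled.

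The cost is SAP wording, a different procedure in the same software and slightly more analysis work; no new data are needed. The downside is reliance on the missing-at-random assumption, which the sensitivity analysis is there to probe. If outcome data have already been examined, date the change and report the planned ANOVA alongside.

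### The Group and Time main effects should not support efficacy conclusions, and comparisons at T1 and T2 adjusted for T0 would use the baseline better than the interaction test

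*Combined protocol and SAP*

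**What the plan says.** All references are to the combined protocol and SAP.

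- **Section 6, Main Analysis.** The mixed ANOVA "will be performed to examine the main effects of" Group and Time, "as well as the Group-by-Time interaction effect on total sedentary time". The three terms are not ranked.
- **Section 6, Post-hoc Testing.** "If a significant interaction is found, Bonferroni-adjusted post-hoc tests will be conducted", comparing the groups at each visit. A significant main effect leads to no further test. No adjustment of these comparisons for T0 is mentioned.
- **Section 6, Significance Level.** "The alpha level is set at 0.05", with no further detail.
- **Section 5.** T0 is baseline, T1 is at 1 month and T2 at 2 months. One of the three levels of Time therefore precedes treatment.
- **Section 2.** "A total of 75 participants are randomly assigned to one of three groups in a 1:1:1 ratio", that is, 25 per arm. Arm 3 receives no intervention.
- **Section 1.** The specific question is "whether motivational support via social media (LINE) provides incremental benefits compared to using a wearable device alone". This compares Arm 1 with Arm 2 after baseline.

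**The concern.** Two of the three terms listed for the main analysis do not answer the trial's question.

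The Group main effect compares arm means averaged over T0, T1 and T2. Randomisation makes the expected difference at T0 zero, so including T0 shrinks the effect. A non-significant Group test could then be misread as no difference between arms.

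The Time main effect is change from visit to visit averaged over all arms, a third of whose participants are untreated. Season, reactivity to being measured and regression to the mean all enter it. A significant Time test could be misread as a benefit of the intervention when controls changed just as much.

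The interaction does address whether change differs between arms, but it spreads its 4 degrees of freedom over every pattern of arm-by-visit differences and treats T0 as one more outcome. The planned between-arm comparisons depend on it. If it is not significant, the Arm 1 against Arm 2 comparison named in the objective has no planned test.

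**Working it through.** The documents give no effect size, SD, correlation, power or dropout rate, so there is no stated calculation to reproduce.

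**Inputs from the documents:** 3 arms, n = 25 each, 3 visits with T0 before treatment, alpha 0.05.

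**Assumed, not in the documents:** SD 1; equal correlation r between any two visits, taken as 0.3, 0.6 and 0.7; complete data; effect d = 0.6 SD in Arm 1 only, the same at T1 and T2.

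**Step 1: what the Group term estimates.** With no effect at T0, an effect d at T1 and T2 enters as (0 + d + d)/3 = 2d/3. An effect at T1 only enters as d/3. This needs no numerical assumption. With d = 0.6, the Group term sees 0.4.

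**Step 2: non-centrality of each three-arm test.**

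- Group (2 and 72 df): 3n × Σ(arm mean − grand mean)² / (1 + 2r). The arm means over visits are 0.4, 0, 0, with sum of squares 0.4² × 2/3 = 0.1067. So 75 × 0.1067 = 8.0, divided by (1 + 2r).
- Interaction (4 and 144 df): n × Σ(interaction residual)² / (1 − r). The sum of squares is 0.6² × (2/3) × (2/3) = 0.16. So 25 × 0.16 = 4.0, divided by (1 − r).
- ANCOVA of the T1–T2 mean on T0 (2 and 71 df): n × Σ(effect − mean effect)² / v, with v = (1 + r)/2 − r². The sum of squares is 0.6² × 2/3 = 0.24. So 25 × 0.24 = 6.0, divided by v, which is 0.56 / 0.44 / 0.36.

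| Test | Non-centrality at r = 0.3 / 0.6 / 0.7 | Power |
|---|---|---|
| Group | 5.00 / 3.64 / 3.33 | 49% / 37% / 34% |
| Interaction | 5.71 / 10.00 / 13.33 | 44% / 70% / 83% |
| T0-adjusted, three arms | 10.71 / 13.64 / 16.67 | 82% / 91% / 95% |

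The last row of power is from simulation (20,000 runs). The non-central F formula, which ignores chance imbalance in T0, gives 83% / 91% / 96%. At each correlation the adjusted test's non-centrality equals the sum of the other two, apart from rounding. The ANOVA splits the evidence between Group and interaction, and adjustment for T0 brings it together.

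**Step 3: the Time term.** Assume no treatment effect and a common drift of 0.3 SD in every arm from T0 to T1 and T2. The visit means are 0, 0.3, 0.3, with sum of squares about their mean 0.3² × 2/3 = 0.06. Non-centrality is 75 × 0.06 / (1 − r) = 6.43 / 11.25 / 15.00 on 2 and 144 df. The Time test is significant in about 61% / 85% / 94% of trials, with nothing due to the intervention.

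**Step 4: another arm pattern.** With effects 0.6 / 0.3 / 0 in Arms 1 / 2 / 3 and r = 0.6, the adjusted test has non-centrality 25 × (0.3² + 0.3²) / 0.44 = 10.23 and power 81%. The interaction has about 56% and Group about 29%. The ordering is unchanged.

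**The case against.** The strongest reply is that the plan already gives the interaction the decisive role. It is tested in the same sentence as the main effects, and it alone opens the between-arm comparisons. A mixed ANOVA yields main effects by default, and examining them is not claiming efficacy from them. Section 5 defines outcomes as change, which points to the interaction. All of this stands: the right randomised term is present, and what is missing is a sentence saying how the main effects may be used.

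Three stronger readings are tempting and are not supported:

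- **That the plan will report a main effect as efficacy.** No text says so. The risk is only that nothing rules it out.
- **That three tests at 0.05 inflate the efficacy error to about 14%** (1 − 0.95³ = 14.3%). This would matter only if any one of the three terms could carry an efficacy claim, and the plan does not provide for that. Under randomisation the Group test also keeps its 5% error. Its fault is dilution.
- **That a baseline-adjusted Arm 1 against Arm 2 contrast always beats the interaction.** A single contrast set against a three-arm omnibus test is not like for like. With effects 0.6 / 0.3 / 0 and r = 0.6, that contrast has about 35% power against 56% for the interaction, because only 0.3 SD separates the two arms. The fair comparison is between three-arm tests, as in the table.

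Two limits remain. At r = 0.3 Group has slightly more power than the interaction (49% against 44%), so Group is not always the weakest test. Also, a test on the T1–T2 mean would halve an effect present at T1 only, which is why each visit should be estimated as well.

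**Conclusion.** The point holds as a cheap improvement of minor to moderate severity. The dilution of the Group effect to 2d/3 and the non-randomised nature of the Time effect follow from the design. That neither should support an efficacy conclusion does not depend on the assumed numbers.

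The gain from adjusting for T0 does depend on assumptions: the effect size, the equal correlation between visits, complete data on 25 per arm, and an effect of similar size at T1 and T2. Within that setting the three-arm adjusted test led at every correlation and in every arm pattern tried. Its advantage over the interaction was about 38 points at correlation 0.3, 21 at 0.6 and 12 at 0.7 (82 − 44, 91 − 70, 95 − 83).

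**What to change.** In section 6, Main Analysis and Post-hoc Testing:

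1. Base efficacy conclusions on between-arm comparisons at T1 and T2 adjusted for T0, by ANCOVA or by a repeated-measures model of T1 and T2 with T0 as covariate.
2. Name the Arm 1 against Arm 2 contrast explicitly, since it is the objective's specific question, and do not make it depend on a significant interaction.
3. Keep the Bonferroni adjustment and state which contrasts and visits it covers.
4. State that the Group and Time main effects and within-arm change are descriptive only.

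The cost is a modest change of model and some rewording of the SAP. No new data, visits or participants are needed, because T0 is already collected.

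### The SAP's only named dependent variable, total sedentary time, is not a listed outcome, and no analysis is prespecified for the primary or secondary measures

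*Combined protocol and SAP*

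**What the plan says.** Section 1 states the aim as evaluating the intervention "on enhancing physical activity (PA) levels and improving sleep quality among adults".

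Section 5 turns this into ranked outcomes. The primary is "Primary Outcome: Change in Physical Activity (measured by steps/day and sedentary breaks", which is two measures with no order between them. The secondary is "Secondary Outcome: Change in Sleep Quality (assessed via standardized sleep quality questionnaires and device-derived sleep metrics", which is two types of measure. All are collected at T0, T1 and T2.

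Section 6 contains one inferential analysis, introduced as "Main Analysis: A Two-way Mixed ANOVA (3 Groups" by three time points. It covers the two main effects, "as well as the Group-by-Time interaction effect on total sedentary time". The follow-up rule is "If a significant interaction is found, Bonferroni-adjusted post-hoc tests will be conducted", and it names no further variable. The descriptive paragraph is limited to baseline: "Baseline characteristics will be summarized as means (SD) or frequencies". On error control across outcomes there is only "The alpha level is set at 0.05".

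**The concern.** The variable to be analysed and the variables declared as outcomes do not match. Total sedentary time is a duration. Sedentary breaks count interruptions of sitting, and steps/day counts steps. By definition these are three different quantities, so a result on sedentary time is not a result on either primary measure and says nothing about sleep.

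What is at stake is prespecification. An analyst who follows Section 6 literally reports on a variable that Section 5 does not rank. An analyst who starts from Section 5 has to decide, with no rule in the plan, which model to use, which measure leads and what alpha each receives. Those decisions could then be made after the results are known. The aim in Section 1, including whether LINE support adds anything to the device alone, would have no confirmatory test behind it.

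**Working it through.** **Step 1: match outcomes to analyses.** Each measure in Section 5 was looked for in Section 6, and each variable in Section 6 was looked for in Section 5.

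| Measure | Rank in Section 5 | Named in Section 6? |
|---|---|---|
| Steps/day | Primary | No |
| Sedentary breaks | Primary | No |
| Sleep questionnaires | Secondary | No |
| Device-derived sleep metrics | Secondary | No |
| Total sedentary time | Not listed | Yes, in the mixed ANOVA |

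Thus 0 of 2 primary measures and 0 of 2 types of secondary measure have a specified analysis, and the 1 variable analysed is not a listed outcome.

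**Step 2: try the other grammatical reading.** The words about sedentary time may belong only to the interaction and not to the main effects. The main effects of group and time would then have no named variable, and steps, breaks and sleep would still have no analysis. The result of Step 1 does not change.

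**Step 3: look for another place that closes the gap.** The post-hoc tests depend on the same ANOVA. The descriptive statistics concern baseline only. No sentence extends the model to other outcomes.

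**Step 4: illustrate why an alpha rule is needed once the primary measures are named.** The plan gives no figure to reproduce here. Inputs: alpha 0.05 (Section 6) and two primary measures (Section 5). Assumption: the two tests are independent.

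- Family-wise error with both at 0.05: 1 − (1 − 0.05)² = 1 − 0.9025 = 0.0975, or 9.75%. Positive correlation lowers it.
- Equal Bonferroni split: 0.05 / 2 = 0.025 each.

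**Step 5: illustrate what a split would cost.** Input: 75 participants in a 1:1:1 ratio (Section 2), so 75 / 3 = 25 per arm. Assumptions, none of them stated in the plan: one two-sided pairwise comparison, 80% power, no dropout, normal approximation, and no further adjustment for several pairs of arms. The detectable standardised difference is (z for two-sided alpha + z for power) × √(2/25), with √(2/25) = 0.2828.

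- Alpha 0.05: (1.960 + 0.842) × 0.2828 = 0.79.
- Alpha 0.025: (2.241 + 0.842) × 0.2828 = 0.87.

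The plan gives no effect size, standard deviation or power, so these values cannot be compared with a design target.

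**The case against.** The strongest reply is that the model is meant for every outcome and sedentary time is only the example given. Section 6 calls the ANOVA the main analysis without saying it is the only one, and data on the listed outcomes are to be collected at all three time points. This part stands: the documents do not show that steps, breaks and sleep will go untested, or that the trial is unable to answer its question. A reader might infer either, but the text supports only that no test of them is prespecified. The reply does not remove the mismatch, because the one variable named is not on the outcome list and so cannot serve as an example of it.

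A second reply is that sedentary time may be the intended outcome and Section 5 the place with the omission. The Move Alert feature in Section 4 is aimed at prolonged sitting, so this is plausible, and the documents do not settle it. If so, Section 5 has to list the variable and give its rank. They also give no ground for ranking steps/day above sedentary breaks or for calling sedentary time exploratory.

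A third reply concerns the error rate. A reader might count three competing primary variables and quote 1 − 0.95³ = 14.3%. That goes too far: Section 5 names only two measures as primary, Section 6 as written tests one variable, and the figure needs three independent tests at 0.05. Even the 9.75% for two measures only illustrates the need for a rule and does not describe the current plan.

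**Conclusion.** The point holds as a contradiction between Sections 5 and 6. It is more than missing detail, because carrying out the plan literally tests an outcome the protocol does not list. Its size is the count: no specified analysis for any of the four listed measures or types of measure. This rests on the text alone and needs no statistical assumption. The 9.75% rests on independence and on both primary measures being tested at 0.05. The detectable differences of 0.79 and 0.87 rest on the assumptions stated with them. The finding does not depend on any of these figures. Because it concerns the primary outcome, it should be resolved before any confirmatory claim is made from the trial.

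**What to change.** Reconcile Sections 5 and 6:

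- In Section 6, name steps/day and sedentary breaks as the dependent variables of the main analysis.
- State how alpha is handled across them, for example 0.025 each, or designate a single measure as primary. Either is acceptable if written down.
- Specify the analysis of both the questionnaire and the device-derived sleep measures, as secondary.
- Either drop total sedentary time or list it in Section 5 with a stated rank.
- State how the activity measures are obtained in Arm 3. Section 4 provides trackers to Arms 1 and 2 only, and the documents do not say how steps or breaks are recorded in the control group. A three-group model needs them in all three arms.

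The cost is mostly SAP rewording. If alpha is split, the detectable standardised difference rises from 0.79 to 0.87 under the assumptions above. The Arm 3 statement is a measurement specification as well as an edit to the SAP. The documents do not say whether outcome data have been analysed. The change should be dated before that happens or, if it already has, disclosed as made afterwards.
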